**Phase II Liver Chemistry Increased Monitoring Criteria with Continued Therapy**

Liver Chemistry Increased Monitoring Criterion and Follow-Up	
Criterion	Actions
ALT $\geq$ 3 x ULN and < 5 x ULN and bilirubin < 2 x ULN, without symptoms believed to be related to liver injury or hypersensitivity, and who can be monitored weekly for 4 weeks	

Notify the sponsor within 24 hours of learning of the abnormality to discuss participant safety.

Participant can continue study treatment

Participant must return weekly for repeat liver chemistry tests (ALT, AST, alkaline phosphatase, bilirubin) until the abnormalities resolve, stabilize or return to baseline.

If at any time, the participant meets liver chemistry stopping criteria, proceed as described in Section 8.

If, after 4 weeks of monitoring, ALT < 3 x ULN and bilirubin < 2 x ULN, monitor participants twice monthly until liver chemistry tests resolve, stabilize, or return to baseline.

AGN-242428

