### Phase II Liver Chemistry Stopping Criteria and Follow-Up Assessments

Liver Chemistry Stopping Criteria	
AST and/or ALT-absolute	AST and/or ALT $\geq 5 \times$ ULN
AST and/or ALT Increase	AST and/or ALT $\geq 3 \times$ ULN persists for $\geq 4$ weeks
Bilirubin or INR	AST and/or ALT $\geq 3 \times$ ULN and TBL $\geq 2 \times$ ULN or INR $> 1.5$
Cannot Monitor	AST and/or ALT $\geq 3 \times$ ULN and cannot be monitored weekly for 4 weeks
Symptomatica	AST and/or ALT $\geq 3 \times$ ULN associated with symptoms (new or worsening) believed to be related to liver injury or hypersensitivity
Potential Hy's Law cases	
AST, ALT, and Bilirubinb	AST and/or ALT $\geq 3 \times$ ULN and TBL $\geq 2 \times$ ULN and alkaline phosphatase $< 2 \times$ ULN

AGN-242428

Required Actions and Follow-up Assessments	
Actions	Follow-Up Assessments

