
AGN-242428

 
Repeat liver chemistry tests (include ALT, AST, ALP, TBL, DBL, IBL, GGT, and LDH) and perform liver chemistry follow-up assessments within 24 to 72 hours.
 
Monitor participants weekly until liver chemistry abnormalities resolve, stabilize, or return to baseline.
 
	
 
globulins.
 
Liver imaging (ultrasound, magnetic resonance, or computerized tomography) and/or liver biopsy to evaluate liver disease; complete the Hy's Law eCRF form and the AESI Form, which is the Adverse Event of Interest Abnormal Liver Function Reporting Form.
 

---	---

AESI = adverse event of special interest; ALT = alanine aminotransferase; AST = aspartate aminotransferase; eCRF = electronic case report form; TBL = total bilirubin; ULN = upper limit of normal

a = New or worsening symptoms believed to be related to liver injury (such as fatigue, nausea, vomiting, right upper quadrant pain or tenderness, or jaundice) or hypersensitivity (such as fever, rash or eosinophilia).

b = All events of AST and/or ALT  $\geq 3 \times$  ULN **and** TBL  $\geq 2 \times$  ULN and alkaline phosphatase  $< 2 \times$  ULN indicate severe liver injury (**potential 'Hy's Law'**) and **must be reported as both an AESI and an SAE** by completing the AESI Form, which is the Adverse Event of Interest Abnormal Liver Function Reporting Form, and sending it to [contact] (or faxing it to the SAE fax number) within 24 hours of learning of the potential Hy's Law case.

c = Includes: Hepatitis A immunoglobulin M (IgM) antibody; hepatitis B surface antigen and hepatitis B Core Antibody (HBcAb); hepatitis C RNA; cytomegalovirus IgM antibody; Epstein-Barr viral capsid antigen IgM antibody (or if unavailable, heterophile antibody or monospot testing); hepatitis E IgM antibody; anti-nuclear antibody; and anti-smooth muscle antibody.

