11.2 CLINICAL LABORATORY PARAMETERS

Descriptive statistics (mean, SD, median, Q1, Q3, minimum, and maximum) for clinical laboratory values (in SI units) and changes from the baseline values at each assessment timepoint will be presented by treatment group for the following laboratory parameters:

Table 11.2-1 Clinical Laboratory Tests

Category ^a	Parameters
Hematology and Coagulation^a	Hematocrit (HCT), hemoglobin (HGB), red blood cell (RBC) count, RBC indices, total leukocyte (or white blood cell [WBC]) count including differential, and platelet count with mean platelet volume, activated partial thromboplastin time (aPTT), prothrombin time (PT), international normalized ratio (INR)
Serum Chemistry	
Electrolytes	Sodium (Na), potassium (K), chloride, bicarbonate
Renal function	Blood urea nitrogen (BUN), creatinine (Cr)
Liver function ^a	ALT, AST, ALP, total, direct, and indirect bilirubin (TBL, DBL, IBL), gamma-glutamyl transferase (GGT), lactate dehydrogenase (LDH)
Pancreatic function	Lipase and amylase
Other ^a (selected tests at Week 6 and Week 10)	Calcium (Ca), magnesium (Mg), phosphorus (P), total protein ^a , albumin ^a , globulins, glucose, uric acid, creatine phosphokinase (CK) ^a , cholesterol (total and fractionated) and triglycerides
Urinalysis	Appearance, bilirubin, color, ketones, glucose, leukocyte esterase, nitrites, pH, blood, protein

^a Visits on Week 6 and Week 10 need random blood draws. Participants can be fasting or non-fasting and only the following laboratory tests will be performed at those visits: Hematology and Coagulation, Liver function, and Other (Total protein, albumin, and CK)

Clinical laboratory test values will be considered potentially clinically significant (PCS) if they meet either the lower-limit or higher-limit PCS criteria listed in [Table 11.2-2](#). A listing of patients with PCS postbaseline values will be provided, including the participant identification (PID) number, baseline, and all postbaseline (including non-PCS) values.

Table 11.2-2 Criteria for Potentially Clinically Significant Laboratory Results

Parameter	Unit	Lower Limit	Higher Limit
CHEMISTRY			
Albumin	g/dL	≤ 2.0	≥ 7.1
Alanine aminotransferase	U/L	—	≥ 3 x ULN
Alkaline phosphatase	U/L	—	> 2 x ULN

Table 11.2-2 Criteria for Potentially Clinically Significant Laboratory Results

Parameter	Unit	Lower Limit	Higher Limit
Amylase	U/L	—	> 1.5 x ULN
Aspartate aminotransferase	U/L	—	≥ 3 x ULN
Bicarbonate	mEq/L	≤ 15	≥ 40

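### Appendix 6 starts weekly monitoring and 24-hour sponsor notice on ALT alone, while every transaminase stopping rule uses AST and/or ALT (minor inconsistency)

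*Protocol*

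**What the plan says.** The last table of Protocol Section 12.6 (Appendix 6) governs participants with raised liver enzymes who continue study treatment. Entry requires "ALT $\geq$ 3 x ULN and < 5 x ULN and bilirubin < 2 x ULN", no symptoms of liver injury or hypersensitivity, and the ability to be monitored weekly for 4 weeks. Two actions follow:

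- The sponsor is told within 24 hours "of learning of the abnormality to discuss participant safety".
- "Participant must return weekly for repeat liver chemistry tests (ALT, AST, alkaline phosphatase, bilirubin) until the abnormalities resolve, stabilize or return to baseline".

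If ALT is below 3 x ULN and bilirubin below 2 x ULN after 4 weeks, the site is to "monitor participants twice monthly until liver chemistry tests resolve, stabilize, or return to baseline". AST is in the panel to be repeated, but not in the entry or step-down criterion.

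The stopping criteria earlier in the same appendix name both enzymes throughout. Two of them bear directly on this point: "AST and/or ALT $\geq 3 \times$ ULN persists for $\geq 4$ weeks" and "AST and/or ALT $\geq 3 \times$ ULN and cannot be monitored weekly for 4 weeks". Table 8-1, the stop rules in Appendix 7, and the AESI definitions (Protocol Section 9.2.8 and Appendix 3; SAP Section 11.1.1) also use AST and/or ALT.

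**The concern.** The stopping rules give AST and ALT equal weight, and the documents offer no reason to treat them differently while the participant stays on drug. The continued-therapy table is the only visible place that orders a visit interval and a notice deadline for someone still taking study medication with a transaminase between 3 and 5 x ULN. If AST cannot open that table, the closer watch is explicit for an ALT-led rise, but for an AST-led rise it depends on inference or site judgment.

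This is participant safety, not inference: no endpoint, power or type I error is affected. It matters somewhat because Protocol Section 5.5 reports ALT/AST elevations in the 4-week proof-of-concept trial, and Section 5.4 presents clear handling of raised liver enzymes as part of the design. About 40 centers will apply the table.

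**Working it through.** There is no plan figure to reproduce. The check traces one case through the rules and then counts visits.

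**Trace.** Two participants on treatment have normal bilirubin, INR at or below 1.5, no symptoms, and weekly visits possible. One has AST 4 x ULN with normal ALT; the other has ALT 4 x ULN with normal AST.

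| Appendix 6 rule | AST 4 x ULN alone | ALT 4 x ULN alone |
|---|---|---|
| Stop: AST and/or ALT at least 5 x ULN | not met | not met |
| Stop: at least 3 x ULN with bilirubin or INR criterion | not met | not met |
| Stop: at least 3 x ULN with symptoms | not met | not met |
| Stop: at least 3 x ULN, weekly monitoring not possible | not met | not met |
| Stop: at least 3 x ULN for 4 weeks or more | not yet met | not yet met |
| Continued therapy: weekly visits, 24-hour notice | **not started** | **started** |

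Only the last row separates the two participants.

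**Step-down.** A participant enters on ALT; AST then rises to 3 x ULN or more during the 4 weeks while ALT falls below 3 x ULN. The ALT-and-bilirubin rule moves this participant to twice-monthly checks, although the Cannot Monitor rule presupposes weekly checks at that AST level. If AST had been raised for the full 4 weeks, the persistence rule would already have stopped treatment. The step-down wording therefore matters only for an AST rise that begins during the 4 weeks.

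**Visit count.** Scheduled visits V = {2, 4, 6, 8, 10, 12, 16} weeks (Protocol Sections 1 and 5.1). For a rise first seen at week s, weekly checks fall at s+1, s+2, s+3 and s+4; the extra checks are those not in V. The 4-week persistence decision is due at s+4, and from scheduled visits alone it falls at the first visit in V at or after s+4.

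| First seen (s) | Extra weekly checks | Number | Decision due | First scheduled visit | Delay |
|---|---|---|---|---|---|
| 2 | 3, 5 | 2 | 6 | 6 | 0 |
| 4 | 5, 7 | 2 | 8 | 8 | 0 |
| 6 | 7, 9 | 2 | 10 | 10 | 0 |
| 8 | 9, 11 | 2 | 12 | 12 | 0 |
| 10 | 11, 13, 14 | 3 | 14 | 16 | 16 - 14 = 2 weeks |
| 12 | 13, 14, 15 | 3 | 16 | 16 | 0 |

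The longest interval between scheduled checks up to the decision is 2 weeks for s = 2 to 8, and 4 weeks (Week 12 to 16) for s = 10 and 12. For s = 12 the decision coincides with the end of treatment, so being on time there has little practical value. A rise first seen at Week 16 is outside the table because treatment has ended.

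The counts assume that the rise lasts the 4 weeks. One first seen at Week 2 and resolved by Week 3 would add 1 check rather than 2.

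**The case against.** The strongest reply is that Appendix 6 already handles this case. Under "AST and/or ALT $\geq 3 \times$ ULN and cannot be monitored weekly for 4 weeks", a participant with AST at 4 x ULN may stay on treatment only if weekly monitoring is possible, so the site has already had to consider weekly checks. On that reading the edit gains no checks, and what is missing is mainly the explicit 24-hour notice. Most of this stands: the rule does presuppose weekly AST checks. But it orders no visit and sets no notice deadline.

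The other replies are weaker, but two of them limit the claim:

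- **Redacted Section 2.** Sections 1 and 5.1 refer to it for laboratory changes that prompt unscheduled visits. It may contain an AST trigger, so no gap in the whole protocol can be claimed. The mismatch inside Appendix 6 would remain.
- **General safeguards.** Section 9 sends immediate safety concerns to the sponsor at once, and Sections 9.2.3 and 9.4.4 require follow-up and repeat of abnormal results. These apply to either enzyme but state no interval.
- **The weekly instruction elsewhere in Appendix 6.** "Monitor participants weekly until liver chemistry abnormalities resolve, stabilize, or return to baseline" is entered on AST and/or ALT, but it sits under actions that begin with stopping treatment. It does not govern a participant who continues.
- **INR.** The entry criterion also omits INR, but INR above 1.5 with a transaminase at or above 3 x ULN meets a stopping rule, and the table sends anyone who meets one to Section 8.

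SAP Section 11.2 says "Clinical laboratory test values will be considered potentially clinically significant (PCS) if they meet either the lower-limit or higher-limit PCS criteria" and sets the same 3 x ULN limit for both enzymes. That defines a listing rather than on-treatment monitoring, so it only supports the view that the enzymes were meant to be treated alike.

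**Conclusion.** The inconsistency is real and minor. The visible text of Appendix 6 gives an isolated AST rise of 3 to below 5 x ULN less explicit monitoring than the same ALT rise.

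The difference is 0 to 3 liver panels per episode, plus the 24-hour notice. The lower end applies if sites already test weekly or Section 2 requires it. The only late persistence decision is for a rise first seen at Week 10, by 2 weeks, and only if no weekly checks are made.

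These figures assume nominal visit days and liver tests at every scheduled visit. Table 9-4 confirms the tests for Weeks 6 and 10; the schedule itself is redacted. Section 5.5 does not describe an AST-only pattern. Rises to 5 x ULN or more, with the bilirubin or INR criterion, or with symptoms are already covered for either enzyme.

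**What to change.** Edit two cells of the continued-therapy table in Appendix 6:

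1. **Entry:** AST and/or ALT at least 3 x ULN, both below 5 x ULN, and bilirubin below 2 x ULN, with the remaining conditions unchanged.
2. **Step-down:** after 4 weeks, AST and ALT both below 3 x ULN and bilirubin below 2 x ULN.

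When making the edit, confirm that the testing criteria in Section 2 agree.

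No threshold moves and no new test is needed, because AST is already in the weekly panel. The cost is 2 to 3 extra panels for an AST-only rise that lasts 4 weeks, and fewer if it resolves early or the site already tests weekly. Section 9 already allows unscheduled safety samples. The same section caps total blood volume at 440 mL including extra assessments, so the added draws should be counted against that limit.

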
 
• Immediately discontinue study treatment.
 
• Report the event to the sponsor within 24 hours.
 
• Complete the liver event eCRF, and complete a serious adverse event (SAE) data collection tool if the event also met the criteria for an SAE.b
 
• Perform liver chemistry follow-up assessments.
 
• Monitor the participant until liver chemistry test abnormalities resolve, stabilize, or return to baseline (see MONITORING).
 
• Do not restart/rechallenge participant with study treatment
 
• As restart/rechallenge is not allowed per protocol, permanently discontinue study treatment and continue participant in the study for any protocol specified follow-up assessments
 
	
 
• Viral hepatitis serology and other laboratory testing, as well as anti-nuclear antibody and anti-smooth muscle antibodyc
 
• Obtain INR and recheck with each liver chemistry assessment until the transaminases values show downward trend
 
• Obtain blood sample for pharmacokinetic (PK) analysis 48 hours after the most recent dosed
 
• Serum creatine phosphokinase (CPK) and lactate dehydrogenase (LDH)
 
• Fractionate bilirubin, if TBL <math>\geq 2 \times</math> ULN
 
• Obtain complete blood count with differential to assess eosinophilia
 
• Record the appearance or worsening of clinical symptoms of liver injury, or hypersensitivity, on the adverse event (AE) report form
 
• Record use of concomitant medications (including acetaminophen, herbal remedies, and other over-the-counter medications) on the concomitant medications eCRF.
 
• Record alcohol use on the liver event alcohol intake eCRF
 
 
If AST and/or ALT <math>\geq 3 \times</math> ULN AND bilirubin <math>\geq 2 \times</math> ULN:
 
 
• Repeat liver chemistry tests (include alanine transferase (ALT), aspartate transaminase [AST], alkaline phosphatase [ALP], total, direct, and indirect, bilirubin [TBL, DBL, IBL], gamma-glutamyl transferase [GGT], and lactate dehydrogenase [LDH]) and perform liver event follow-up assessments within 24 hours.
 
• Monitor participant twice weekly until liver chemistry test abnormalities resolve, stabilize, or return to baseline.
 
• A specialist or hepatology consultation is recommended.
 
 
If AST and/or ALT <math>\geq 3 \times</math> ULN AND bilirubin <math>< 2 \times</math> ULN:
 
 
• Type 1 anti-liver kidney microsomal antibodies, and quantitative total immunoglobulin G (IgG) or gamma
 

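### Appendix 6's table for continuing drug through a moderate transaminase rise has no INR condition and no weekly INR, although INR above 1.5 is part of a stopping criterion

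*Protocol*

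**What the plan says.** Appendix 6 of the protocol has two tables for raised transaminases.

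The first lists stopping criteria. One combines AST and/or ALT of at least 3 × ULN with either total bilirubin of at least 2 × ULN or INR above 1.5. Two others are "AST and/or ALT $\geq 3 \times$ ULN persists for $\geq 4$ weeks" and AST and/or ALT of at least 3 × "ULN and cannot be monitored weekly for 4 weeks". Table 8-1 and Appendix 7 repeat the bilirubin-or-INR criterion. Section 9.2.8 makes the same combination an adverse event of special interest, and SAP Section 11.1.1 summarises it by treatment group. Once a stopping criterion is met, the follow-up includes this: "Obtain INR and recheck with each liver chemistry assessment until the transaminases values show downward trend".

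The second table covers increased monitoring on continued therapy.

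- **Entry:** "ALT $\geq$ 3 x ULN and < 5 x ULN", with bilirubin below 2 × ULN, no suggestive symptoms, and the ability to attend weekly for 4 weeks.
- **Actions:** the sponsor is told within 24 hours; "Participant can continue study treatment"; and "Participant must return weekly for repeat liver chemistry tests (ALT, AST, alkaline phosphatase, bilirubin) until the abnormalities resolve, stabilize or return to baseline". If a stopping criterion is met at any point, Section 8 applies.
- **Step-down:** the rule opens "If, after 4 weeks of monitoring, ALT" and sets limits for ALT (below 3 × ULN) and bilirubin (below 2 × ULN) only. Checks then become twice monthly.

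Table 9-4 places INR under hematology and coagulation, not under liver function. Its footnote a keeps coagulation in the reduced panel at Weeks 6 and 10. Section 2, which holds the schedule and the criteria for unscheduled testing, is redacted.

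**The concern.** The second table governs people who have a known transaminase rise and are still taking the drug. Its weekly checks should supply every laboratory value needed to tell whether a stopping criterion has been met. They supply the transaminases and bilirubin but not INR. A symptomless participant with ALT 4 × ULN, normal bilirubin and INR 1.6 fits both the continue rule and a stopping criterion. The override settles that conflict only if an INR has been drawn.

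The order is also odd: someone who has stopped the drug has INR rechecked with each liver assessment, while someone still taking it does not, as far as this table goes.

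What is at stake is safety monitoring. Section 5.5 reports ALT/AST elevations at one dose in the earlier 4-week study, and this trial doses for 16 weeks. An INR-based stopping event that develops between scheduled visits could be seen late. The matching adverse event of special interest relies on values from one sample, or from samples within 24 hours, so a weekly check without INR cannot register its INR limb.

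**Working it through.** The plan gives no figure to reproduce. The check compares the two tables and then counts visits.

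**1. The two tables side by side (Appendix 6)**

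| Element | Stopping criteria | Monitoring on drug |
|---|---|---|
| Transaminase | AST and/or ALT | ALT only, at entry and step-down |
| Bilirubin limit | 2 × ULN | 2 × ULN |
| INR limit | above 1.5 stops | none |
| Repeat tests | INR with each liver chemistry assessment | ALT, AST, alkaline phosphatase, bilirubin |

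The term liver chemistry cannot be stretched to include INR. Table 9-4 classes INR with coagulation, and the post-stopping actions ask for it in addition to liver chemistry.

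**2. Laboratory patterns**

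Take symptomless participants who can attend weekly, before the 4-week persistence rule applies. Use three bands for ALT and for AST (below 3, 3 to below 5, at least 5 × ULN), two for bilirubin (below 2, at least 2 × ULN) and two for INR (up to 1.5, above 1.5).

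- All patterns: 3 × 3 × 2 × 2 = 36.
- Patterns meeting the continue criterion: 1 × 3 × 1 × 2 = 6.
- Of those 6, patterns that also meet a stopping criterion: 3 with INR above 1.5, plus 1 with INR up to 1.5 and AST of at least 5 × ULN, giving 4.
- Patterns with a transaminase of at least 3 × ULN that meet neither: 1 (AST 3 to below 5 × ULN, ALT below 3 × ULN, bilirubin below 2 × ULN, INR up to 1.5).

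The AST overlap shows itself, because AST is in the weekly panel. The INR rise in the other three shows only if INR is drawn. These are counts of patterns, not of participants.

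**3. Weekly checks without a required INR**

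Visits are at Weeks 2, 4, 6, 8, 10, 12 and 16 (Section 5.1). Assume INR at each of them. A rise found at Week w is checked at w+1 to w+4.

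| Found at Week | Checks at Weeks | With INR | Without INR |
|---|---|---|---|
| 2 | 3, 4, 5, 6 | 4, 6 | 2 of 4 |
| 4 | 5, 6, 7, 8 | 6, 8 | 2 of 4 |
| 6 | 7, 8, 9, 10 | 8, 10 | 2 of 4 |
| 8 | 9, 10, 11, 12 | 10, 12 | 2 of 4 |
| 10 | 11, 12, 13, 14 | 12 | 3 of 4 |
| 12 | 13, 14, 15, 16 | 16 | 3 of 4 |

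**4. Delay against weekly INR**

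Delay in days = 7 × (week of the next required INR − week of the first weekly check at which the INR would be high). This supposes that the transaminase rise and the high INR both last until that INR. If either falls back sooner, the event is missed rather than late.

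- Found at Weeks 2 to 8: the worst case is one week short of a visit, for example 7 × (4 − 3) = 7 days.
- Found at Week 10, INR high by Week 11: 7 × (12 − 11) = 7 days.
- Found at Week 10, INR high by Week 13: the next scheduled visit is Week 16, but by Week 14 the rise has lasted 4 weeks. If AST or ALT is still at least 3 × ULN, the persistence criterion is met and INR is then required: 7 × (14 − 13) = 7 days. If both are lower, the INR criterion cannot be met.
- Found at Week 12, INR high by Week 13: 7 × (16 − 13) = 21 days. Week 16 is also the end of treatment.

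**The case against.** The strongest reply is that the table does not stand alone. It yields to the stopping criteria at any time. Its first action brings in the sponsor within 24 hours to discuss safety, and INR can be ordered then. Section 9.4.4 allows extra tests at any time and calls for clinically significant abnormal results to be repeated. Scheduled visits supply some INRs, including, under the assumption used here, one at entry for a rise found at such a visit. Section 2 is redacted and may require INR at unscheduled visits. In addition, Section 8.1 ties withdrawal to relatedness, and footnote c of Table 8-1 leaves liver-related discontinuation to the investigator's consideration, so a high INR would not end treatment automatically under that section.

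All of this stands as mitigation, and it limits the claim to the visible text of Appendix 6. It does not remove the mismatch. The override needs an INR value, the sponsor contact does not itself require one, and the repeat rule does not reach an INR that was normal at entry. If Section 2 does require INR, an explicit list without it still misleads sites.

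Three stronger readings are tempting, and the documents do not support them:

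- A reader might infer that the protocol tells sites to keep a participant with a known INR above 1.5 on drug. It does not, because the override directs them to Section 8.
- A reader might infer that the table ignores AST. AST is in the weekly panel. The stops for a rise that cannot be followed weekly, or that lasts 4 weeks, apply to AST and already imply weekly follow-up of an isolated AST rise. What remains is drafting: entry and step-down name only ALT, so falling ALT with AST still at least 3 × ULN at 4 weeks fits the step-down wording while meeting the persistence stop.
- A reader might infer a three-week delay in general. The persistence rule rules that out for every entry week except Week 12.

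**Conclusion.** The point holds for INR. The table for participants kept on drug has no INR condition at entry or step-down and no INR in its weekly panel, while INR above 1.5 with a transaminase of at least 3 × ULN is a stopping criterion. The ALT-only wording is a secondary drafting point.

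With INR at every scheduled visit, 2 of 4 weekly checks lack a required INR for a rise found at Weeks 2 to 8, and 3 of 4 for one found at Week 10 or 12. Detection could be up to about 7 days later for entry at Weeks 2 to 10, and up to 21 days later only for entry at Week 12. Table 9-4 confirms coagulation by name only at Weeks 6 and 10. INR at the other visits is an assumption, though a natural one, since Weeks 6 and 10 are the reduced-panel visits. The figures also suppose that the rise lasts through four weekly checks.

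The visible documents do not support an estimate of how many participants would enter this table, so no participant count is given. The primary endpoint, its analysis and the sample size are unaffected. This is a cheap improvement, not a flaw that threatens the trial.

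**What to change.** Make three changes in the Appendix 6 increased-monitoring table:

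1. **Entry:** AST and/or ALT ≥ 3 × ULN with both below 5 × ULN, bilirubin below 2 × ULN and INR ≤ 1.5. Keep the existing conditions on symptoms and weekly attendance.
2. **Weekly repeat tests:** add INR.
3. **Step-down:** AST and ALT both below 3 × ULN, bilirubin below 2 × ULN and INR ≤ 1.5.

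The cost is one coagulation tube at the 2 to 3 weekly checks per monitored participant that would otherwise lack INR. At an assumed 2.7 to 4.5 mL per tube, that is 2 × 2.7 = 5.4 mL to 3 × 4.5 = 13.5 mL. Against the 440 mL limit in Section 9, this is 5.4/440 = 1.2% to 13.5/440 = 3.1%. For participants already in the table, these checks take place anyway. An isolated AST rise would need 2 to 3 weekly visits outside the schedule, which the cannot-monitor stop already implies.

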### Overall Study Design:

This is a double-blind, randomized, placebo-controlled trial to evaluate the efficacy, safety, tolerability, pharmacokinetics and pharmacodynamics of AGN-242428 when administered once-daily for 16 weeks to adults with moderate to severe plaque psoriasis. The study consists of 3 periods, as described below. Details of individual assessments to be completed at each study visit are included in Section 2.

**Screening Period:** The purpose of the screening period is to evaluate potential study participants and to qualify them for enrollment into the study. This period begins at the point of informed consent and ends when the participant is randomized to treatment. The screening period will be up to 4 weeks ( $\leq 28$  days) in duration.

**Treatment Period:** Participation in the study begins at the point the participant is randomized. The treatment starts after his/her first dose of study medication and ends after 16 weeks of treatment or at the point of permanent study medication withdrawal should the participant discontinue treatment prior to completion of Week 16.

[figure not shown]
On Day 1 of the treatment period, qualified participants will be randomly assigned to receive 16 weeks of once-daily oral treatment with [REDACTED] AGN-242428, [REDACTED] AGN-242428, [REDACTED] AGN-242428, or placebo. Baseline data for evaluation of participant efficacy and safety will be obtained on Day 1, prior to receiving the first dose. Participants will complete study visits on the first day of treatment and following 2, 4, 6, 8, 10, 12 and 16 weeks of treatment for evaluation of efficacy, safety and tolerability assessments.

A subset of approximately 14 to 18 participants in each treatment group (includes placebo), who have provided consent, will have sequential blood samples collected at scheduled times before and up to 24 hours after study medication administration during the Week 4 visit to establish AGN-242428 pharmacokinetic (PK) concentration versus time profiles. All participants will have blood samples collected to determine trough AGN-242428 concentrations obtained on Day

AGN-242428

1 and at the Week 4, 8, 12 and 16/early termination visits. Random time PK sampling at Weeks 6 and 10 (in addition to other assessments eg, select laboratory tests [see [Table 9-4](#)] and AEs [Section [9.2](#)]) will also be obtained in all participants.

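### Appendix 6 can be read as ending weekly liver tests at a steady ALT of 3 to <5 x ULN on treatment, although 4-week persistence at that level is a stopping criterion, one that Section 8 does not list

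*Protocol*

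**What the plan says.** Protocol Appendix 6 (12.6) has two boxes that bear on this point.

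- **Stopping criteria.** One row is AST and/or ALT >= 3 x "ULN persists for $\geq 4$ weeks". Another stops a participant with AST and/or ALT >= 3 x "ULN and cannot be monitored weekly for 4 weeks".
- **Increased monitoring with continued therapy.** This covers ALT >= 3 and < 5 x ULN with bilirubin < 2 x ULN and no related symptoms, in a participant "who can be monitored weekly for 4 weeks". It states "Participant can continue study treatment" and sets the end of weekly testing: "Participant must return weekly for repeat liver chemistry tests (ALT, AST, alkaline phosphatase, bilirubin) until the abnormalities resolve, stabilize or return to baseline". A later bullet, opening "If, after 4 weeks of monitoring", moves participants with ALT < 3 x ULN and bilirubin < 2 x ULN to twice-monthly tests. On stopping, the box says "If at any time, the participant meets liver chemistry stopping criteria, proceed as described in Section" 8.

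In Section 8, Table 8-1 lists three liver criteria: transaminases >= 5 x ULN; >= 3 x ULN with raised bilirubin or INR; and >= 3 x ULN with symptoms. The stop rules in Appendix 7 (12.7) list the same three. Neither has a 4-week persistence criterion.

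The Synopsis places visits on Day 1 and "following 2, 4, 6, 8, 10, 12 and 16 weeks of treatment for evaluation of efficacy, safety and tolerability assessments". Table 9-4 confirms liver function tests at Weeks 6 and 10. The full schedule, and the testing criteria that Section 2 is said to hold, are redacted.

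**The concern.** The end rule for weekly testing offers three alternative outcomes. Because stabilizing is listed beside resolving and returning to baseline, it naturally covers values that are steady but still abnormal. A course such as 3.5, 3.6, 3.5 x ULN (an illustration) would qualify. The same course is also moving towards the persistence stop. One participant can therefore meet the exit from weekly testing while the 4-week clock is still running and dosing continues.

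Elsewhere in Appendix 6, nearly the same end rule applies after study drug has been stopped. There it is harmless, because no persistence clock is running.

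What is at stake is consistent handling of a recognised risk. Section 5.5 reports transaminase elevations at one proof-of-concept dose level and not at another. Section 5.4 relies on well-defined processes for liver enzyme elevations as part of safety monitoring. With about 40 centers and no definition of stabilize, sites may end weekly tests at different times. A site that follows the cross-reference to Table 8-1 will not find the persistence stop there.

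**Working it through.** The plan gives no figure to reproduce. The check is a comparison of text, then visit arithmetic.

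**1. Does any sentence fix 4 weeks of weekly tests?**

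- The entry condition and the cannot-monitor stop concern whether weekly tests for 4 weeks are feasible.
- The step-down bullet presupposes 4 weeks of monitoring, but covers only ALT that has fallen below 3 x ULN.
- The only sentence that says when weekly tests end is the quoted one, and it allows an earlier end.
- No bullet in the box says what happens if ALT is still 3 to <5 x ULN at 4 weeks.

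**2. Does the cross-reference lead to the persistence stop?**

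| Liver criterion | Appendix 6 | Table 8-1 | Appendix 7 |
|---|---|---|---|
| >= 5 x ULN | yes | yes | yes |
| >= 3 x ULN with bilirubin or INR | yes | yes | yes |
| >= 3 x ULN with symptoms | yes | yes | yes |
| >= 3 x ULN for >= 4 weeks | yes | no | no |
| >= 3 x ULN, weekly tests not possible | yes | no | no |

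Section 8.1 does point back to Appendix 6, but as suggested actions, so the reader is sent in a circle.

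**3. How late could the stop be found?**

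Inputs: visits at Weeks 2, 4, 6, 8, 10, 12 and 16 (Synopsis; Section 5.1). Assumptions: liver tests at each of these visits (only Weeks 6 and 10 are confirmed), nominal weeks without visit windows, and a first elevation found at a scheduled visit. For illustration, a plateau is called after two weekly repeats; the protocol gives no definition.

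Let t be the week of the first value >= 3 x ULN.

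- Persistence point: P = t + 4.
- Detection: V = first scheduled visit at or after P. Delay = V - P.
- Release from weekly tests: R = t + 2. Untested interval = next scheduled visit after R, minus R.

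| t | P | V | Delay (weeks) | R | Next visit after R | Untested (weeks) |
|---|---|---|---|---|---|---|
| 2 | 6 | 6 | 0 | 4 | 6 | 2 |
| 4 | 8 | 8 | 0 | 6 | 8 | 2 |
| 6 | 10 | 10 | 0 | 8 | 10 | 2 |
| 8 | 12 | 12 | 0 | 10 | 12 | 2 |
| 10 | 14 | 16 | 2 | 12 | 16 | 4 |
| 12 | 16 | 16 | 0 | 14 | 16 | 2 |

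Only t = 10 gives a delay: 16 - 14 = 2 weeks, with 16 - 12 = 4 weeks untested. Detection then falls at Week 16, when treatment ends anyway. If weekly tests ran the full 4 weeks, the same participant would be tested at Weeks 11, 12, 13 and 14, and the delay would be 0.

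**The case against.** The strongest reply is that the box, read as a whole, already means weekly tests for 4 weeks. Continued dosing is open only to a participant who can be tested weekly for that long, inability to do so is itself a stop, and the step-down starts after 4 weeks. The opposite reading is also odd: a participant at 3.5 x ULN could be released after two repeats, while one who fell below 3 x ULN after 4 weeks would still be tested twice a month. This stands as good evidence of intent. It does not supply the missing sentence.

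Other safeguards can be read in the protocol:

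- Section 9.4.4 asks for clinically significant laboratory values to be repeated until they normalise, return to baseline or cease to be clinically significant. It has no exit for stable values, but it depends on judgement and sets no interval.
- The box requires contact with the sponsor within 24 hours.
- Investigators may add unscheduled visits at any time.
- Table 8-1 allows a stop on medical judgement.
- Section 2 is said to hold testing criteria for predefined laboratory changes. They are redacted, so whether they close the gap cannot be judged.

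A reader might infer that the plan releases persistent elevations from testing and that they go undetected, or that the released participant is the one most likely to meet the stop. The documents support neither. Scheduled visits would still show most plateaus on time, and no figure in the documents bears on who is most likely to reach the persistence stop.

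**Conclusion.** The point holds as a conflict of wording in a safety rule. Appendix 6 can be read as ending weekly tests at a plateau that its own persistence criterion is meant to detect, and the Section 8 pointer leads to a table without that criterion. It does not show that fewer than 4 weeks of tests were intended.

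The size is limited. Under the stated visit assumption, a first elevation at Week 2, 4, 6, 8 or 12 has a visit exactly 4 weeks later, so detection of the stop is not delayed. Only onset at Week 10 is exposed: no test from Week 12 to Week 16 if a plateau is called by Week 12, and the Week 14 persistence point found 2 weeks late. These figures rest on liver tests at every visit named in the text, on an illustrative plateau call, and on no help from the redacted Section 2 criteria. An elevation first seen at an unscheduled visit lies outside this check. The correction is worth making because it is cheap and the risk is one that the protocol itself recognises.

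**What to change.** Reconcile the two Appendix 6 boxes (stopping criteria; increased monitoring with continued therapy), Table 8-1 and the Appendix 7 stop rules:

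- State whether a value that has levelled off at >= 3 x ULN on treatment ends weekly testing or continues to be followed against the 4-week persistence criterion.
- State what applies when ALT is still >= 3 x ULN after 4 weeks.
- Make the weekly-test exit, the 4-week step-down and the persistence stop follow one consistent rule.
- Make the Section 8 cross-reference lead to that rule, so that Section 8, Appendix 6 and Appendix 7 agree.

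The sponsor's medical team decides what the rule is; none is proposed here. The change is a short edit to these places, by amendment or with a clarification to sites. The downside is possibly a few more liver tests in a small number of participants.
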